Second, we developed a printed handout to augment verbal information. In an RCT of 60 women hospitalized for preterm birth, the control group received verbal information from a clinician and the intervention group additionally received a printed handout. Knowledge of long-term outcomes was higher in the intervention group, (71% vs 45%, P=0.02). This evidence-based printed handout was recognized in the 2015 American Academy of Pediatrics (AAP) Periviability Practice Guidelines. Despite benefit in limited trials, printed information has failed to have a wider impact due to difficulties in dissemination and scalability.

We then developed the P3 mobile education as multimedia information improves learning and digital tools decrease logistic challenges. Obstetricians in our hospital system introduced the P3 education to 31 parents at the time of diagnosis of a risk factor for preterm birth. The P3 mobile education was downloaded to the participant smartphone from Apple store or Google play. The median (range) GA at enrollment was 20 (18-22) weeks. Four weeks after enrollment, 28 participants (18 mothers and 10 fathers) completed the final survey. GA at birth is known for 15 of the 18 mothers, with 6 (40%) experiencing preterm birth between 22-36 weeks GA. Among the 15 participants for whom utilization data is available, over the 4 weeks of participation, the P3 mobile education was accessed for a total of 118.5 hours, with range of 6 minutes to 14 hours per participant. Participants reported receiving more information from the P3 mobile education than from their healthcare provider, in the areas of preterm labor, premature infants and parental role and responsibilities.

	Select survey items and participant responses	Yes (%)
Medical knowledge		
1. Did the app provide new information to you?		100
2. Was some of the information given in the app important for you to know?		100
3. Because of the app, do you feel better prepared if you were to have a premature infant?		100
4. In your opinion, will this app benefit families?		100
5. Did the app inform you about difficulties that a premature baby may face at birth?		89
Emotional health		
1. Did the app make you feel more aware of your risk for having a premature delivery?		93
2. Did the app increase your anxiety unnecessarily?		14
3. As time passed and you were familiar with the information provided, did the app increase your anxiety about having a premature infant later?		21

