##### Enrollment and consent.

- 1) The clinical research assistant (CRA) will screen daily obstetric clinic appointments to identify potentially eligible parents.
- 2) The obstetric provider will introduce the study to eligible parents and refer interested parents to the CRA.

**3)** The CRA will meet with the parents and invite all eligible pregnant women (or minors) and present partners to participate. For partners who are not present at the time of the obstetric clinic appointments, the pregnant women (or minors) will be asked if they have a support person for this pregnancy. If so, they are asked if they would be willing to provide this person's contact information. If they offer the information, these partners will be contacted and invited to join the study by the CRA, with consenting process through REDCap.

**4)** As part of the consent process, parents will be provided detailed study information, the risks to confidentiality, the risk of heightened anxiety, the extent of researcher access to health records, as well as what will happen to data already collected should the participant withdraw from the study. Parents who decline participation will continue to receive standard pregnancy and prenatal care. Participants will also be asked during the enrollment process if the CRA can add P3 study as a contact in their phone, so that the CRA office number, the study phone number, and the study email are in the participants' phone.

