##### Data collection. (Please see Survey Schedule in Section 52.)

At baseline (16-21 weeks) the CRA will administer the *health literacy assessment*, will ask participants to self-administer the *Entry Questionnaire*, an *anxiety measure*, and a subjective *global health measure*, and will abstract *maternal clinical data* and *reproductive history* from the medical record.

As pregnancy continues, REDCap will automatically send out questionnaires to participants at key time points: the start of their 25th, 30th, and 34th weeks. These times will include *Prematurity Knowledge Questionnaires* (specific to their gestational age), a *Preparation for Decision Making scale*, and an *anxiety measure*. At these time points, if they do not complete the questionnaire the first day they are sent it, they will

be sent an automatic reminder through REDCap for the next 2 days. If the participant still has not completed the questionnaire by this time, the CRA will contact the participant by phone.

At study completion, within two weeks of either preterm childbirth or completion of the 34 week questionnaire, participants will be asked to also complete the *Educational-Aid Questionnaire*.

Participants will receive \$20 for each completed follow-up assessment (up to \$80) and entered into a lottery to win an additional \$50 for every questionnaire they return the day they were sent it.

Data will be collected and managed using the REDCap (Research Electronic Data Capture) system. This system is a secure, web-based application designed to support data collection for research. It provides data validation, audit trails, and automated export procedures to statistical packages. Branching logic and calculated fields can also be created in the system to support data entry.

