### **Data Analysis**

[name] will perform 1) blinded scoring of the Prematurity Knowledge Questionnaire using prespecified rules for each response, and 2) blinded analysis with masked group assignment in the dataset. The randomized design, the blinded scoring, and the blinded comparison of post-intervention NICHD recommended knowledge between the P3 and ACOG groups should achieve robust and unbiased results. The Educational-Aid Questionnaire responses and the P3 tracking data will be analyzed separately after completion of the other analyses.

Statistical analyses will be conducted in SAS. The primary outcome is the knowledge score for long-term outcomes (cerebral palsy, learning problems, behavior problems, chronic lung disease, blindness, and hearing impairment), and the primary analysis will use Student's t-test to compare the two groups on knowledge of long-term outcomes at 25 weeks. We will use regression methods to examine relationships between knowledge and sociodemographic characteristics, health literacy level, and the mobile intervention use pattern captured by the P3 software. Additional planned analyses will compare knowledge at later time points and in the other NICHD-recommended domains, e.g. short-term outcomes, as well as differences between groups in preparation for decision-making scores and anxiety scores. We will also use regression methods to examine relationships between knowledge and sociodemographic characteristics, health literacy level, and the mobile intervention use pattern captured by the P3 software.

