### **Aim 2: Determine the effect of the P3 mobile app on parental preparation for decision-making.**

Study procedure, participants, and data management are the same as described for Aim 1.

*Data collection.* Participant decision self-efficacy will be assessed at study entry and exit. Preparation for decision-making and anxiety will be in conjunction with the knowledge questionnaire at 25, 30 and 34 weeks.

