### **Study measures**

*Decision Self-Efficacy Scale* is an 11-item scale that measures self-confidence or belief in one's abilities in decision-making, including shared decision-making.

*Preparation for Decision Making scale* is a 10-item scale that assesses how useful a decision-support intervention is in preparing the respondent to communicate with their clinician about a health decision. It has been shown to discriminate between patients who did and did not find a decisional aid helpful with a difference of 0.6 points on a 1-5 scale, and  $SD \approx 1.0$ . It can be customized to represent the particular intervention and decision under consideration; in this case, decisions about resuscitation, hospital choice, and breastfeeding are focused on during appropriate time points.

*PROMIS Anxiety Computerized Adaptive Test (CAT)* measures general anxiety over the past seven days. With CAT administration, participant responses guide the system's choice of subsequent items to enable a highly precise score with just ~5 items answered for most participants. PROMIS measures have evidence for validity in the general population and provide a T-score, where 50 (SD 10) corresponds to the US average.

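### Anxiety is measured at baseline, but the between-group anxiety comparison names no method and gives the baseline score no role, so available precision may go unused

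*Combined protocol and SAP*

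**What the plan says.** Baseline collection is stated in the Aim 1 Data collection section: the research assistant "will ask participants to self-administer the *Entry Questionnaire*, an *anxiety measure*, and a subjective *global health measure". The Aim 2 data collection paragraph gives the follow-up times: "Preparation for decision-making and anxiety will be in conjunction with the knowledge questionnaire at 25, 30 and 34 weeks". The only anxiety instrument described is the PROMIS Anxiety CAT (Aim 2, Study measures). It covers the past seven days, and PROMIS measures "provide a T-score, where 50 (SD 10) corresponds to the US average".

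The Enrollment and consent section has parents told of "the risk of heightened anxiety". The pilot survey table in the Background has two relevant items: "Did the app increase your anxiety unnecessarily" (14% yes) and "did the app increase your anxiety about having a premature infant later" (21% yes).

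The analysis of anxiety is one clause in the Aim 1 Data Analysis section, among the additional planned analyses: "as well as differences between groups in preparation for decision-making scores and anxiety scores". It gives no test, covariate, main time point or size of difference that would matter. Student's t-test is named for 25-week knowledge (Aim 1) and for preparation for decision making (Aim 2). The regressions in the two analysis sections concern knowledge and preparation scores, not anxiety.

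**The concern.** The question about anxiety is whether the P3 education raises it. Each woman's anxiety before the education is among the most informative things to know when answering that, and the plan already collects it. Nothing in the analysis text uses it.

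Two things are at stake. First, if anxiety at entry predicts anxiety later, leaving it out of the model leaves explainable variation in the error term. The confidence interval is then wider than it need be, on an outcome where a wide interval makes a real rise easy to miss. Second, randomisation is stratified by gestational age at enrolment only, so the arms can differ by chance in entry anxiety. An unadjusted comparison cannot separate that difference from an effect of the education.

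An unstated method also leaves the choice between adjusted and unadjusted analysis open until the data are seen.

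**Working it through.** **Inputs from the documents.** 1:1 allocation (Randomization); 50 analysed per group (Sample Size); T-score SD 10, a US reference value (Aim 2, Study measures).

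**Assumptions.** The baseline anxiety measure is the same PROMIS instrument. The trial SD is 10, with 8 as a check. The baseline-to-follow-up correlation r is 0.3, 0.5 or 0.7; the documents give none.

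**The plan's own figure.** For knowledge, n per group = 2 × (1.960 + 0.842)² × (35/20)² = 48.1, so 49; 50 per group gives 81 to 82% power for 20 points. The stated 50 reproduces. No figure is stated for anxiety.

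**Unadjusted anxiety comparison.**
- SE = 10 × √(2/50) = 2.0 points.
- 95% CI half-width = 1.984 × 2.0 = 3.97, about 4.0.
- Detectable difference at 80% power, two-sided 0.05: (1.960 + 0.842) × 2.0 = 5.60 by the normal formula, 5.66 by the t distribution.

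**Baseline-adjusted comparison.** The residual SD is 10 × √(1 − r²), so the half-width and detectable difference shrink by √(1 − r²). The equivalent gain in sample size is 1/(1 − r²). The lost degree of freedom is negligible here. The half-width and detectable difference below are t-based; power uses the normal formula.

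| r | √(1 − r²) | CI half-width | Detectable difference | Equivalent extra women | Power for a true 4-point rise |
|---|---|---|---|---|---|
| unadjusted | 1 | 4.0 | 5.7 | – | 52% |
| 0.3 | 0.954 | 3.8 | 5.4 | 10% | 55% |
| 0.5 | 0.866 | 3.4 | 4.9 | 33% | 64% |
| 0.7 | 0.714 | 2.8 | 4.0 | 96% | 80% |

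With SD 8 the detectable difference is 4.5 unadjusted, and 4.3, 3.9 or 3.2 adjusted.

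**Chance imbalance.** The baseline difference between arms also has SD 10 × √(2/50) = 2.0 points. A difference above 3 points in either direction has probability 2 × (1 − Φ(3/2.0)) = 13%. With equal SDs, the expected shift in the unadjusted contrast is r times the imbalance: a 2-point imbalance shifts it by 0.6, 1.0 or 1.4 points at r = 0.3, 0.5 or 0.7.

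**Simulation** (20,000 trials per setting, 50 per arm, SD 10, r = 0.5 and 0.7):
- No true effect, all trials: the unadjusted test rejects in 5.2% and 5.0%, and the adjusted test in 5.1% and 4.8%.
- No true effect, P3 more than 3 points higher at baseline: unadjusted 12% and 20%; adjusted 4% and 5%.
- True 4-point rise, P3 more than 3 points lower at baseline: unadjusted power 16% and 5%; adjusted 60% and 79%.

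**Change score as an alternative.** Its SD is 10 × √(2 − 2r). By the normal formula the detectable difference is 6.6, 5.6 or 4.3 at r = 0.3, 0.5 or 0.7, against 5.6 for the plain comparison. It is worse than ignoring baseline at 0.3 and no better at 0.5.

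**The case against.** The strongest reply is that anxiety is an additional analysis in a randomised trial, and that the plan does not rule out adjustment. Much of this stands.

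- A reader might infer that the unadjusted comparison is biased, or that imbalance passes in full into the result. Neither is supported. Under 1:1 randomisation the contrast is unbiased with correct overall type I error, as the simulation shows. Imbalance matters only conditionally, and only a fraction r of it passes through.
- A reader might infer that the plan commits to an unadjusted t-test for anxiety. It does not; the method is unstated, and the t-test reading is drawn from the other outcomes.
- A reader might treat PROMIS Anxiety as a stable trait and expect a high correlation. The documents describe a seven-day measure. Baseline falls at 16 to 21 weeks and follow-up runs to 34, a gap of roughly 4 to 18 weeks, so a value such as 0.3 is plausible and the gain would then be modest.
- A reader might infer that a non-significant result will be presented as reassurance. No section says so, and no safety conclusion is planned. Staff are also trained by a perinatal psychologist to recognise anxiety and to address or refer it, so individual distress does not depend on this comparison.
- The pilot figures are uncontrolled self-reports. If all 28 final-survey completers answered, they are about 4 and 6 people (0.14 × 28 and 0.21 × 28).
- The Aim 2 paragraph omits baseline anxiety, but Aim 2 follows the Aim 1 procedure, which includes it. This is clerical, not a gap in collection.

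None of this gives a reason to leave the baseline score unused. Adjustment improves precision at every correlation examined.

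**Conclusion.** The point holds as a matter of specification and precision. The plan collects baseline anxiety, compares anxiety between groups, names no method and does not connect the two. With 50 per arm and SD 10, using the baseline score narrows the CI half-width from 4.0 points to 3.8, 3.4 or 2.8 as r runs through 0.3, 0.5 and 0.7. It also protects the result against a chance imbalance whose SD is 2.0 points.

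The size of the gain rests on a correlation and a trial SD that the documents do not give, and on the baseline measure being the PROMIS instrument. Its direction does not depend on the exact value of r, provided baseline and follow-up are correlated well enough to repay one degree of freedom. It would be too strong to say that adjustment settles whether P3 raises anxiety. The detectable difference remains 4.0 to 5.4 points, smaller rises could not be excluded, and the documents state no difference that would count as material.

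**What to change.** In the Aim 1 Data Analysis section, state that the PROMIS Anxiety T-score in pregnant participants will be analysed at each of 25, 30 and 34 weeks by linear regression on arm, with the baseline T-score as covariate. Report the adjusted P3 minus ACOG difference with its 95% CI, say that a higher score is worse, and state that p > 0.05 will not be taken as evidence of no harm. If the investigators want to draw a conclusion from the upper confidence limit, they must first state the difference they regard as material; without it the limit gives no decision rule. A plain change from baseline should not replace the covariate.

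For consistency, name the baseline anxiety instrument in the Aim 1 Data collection section and add baseline to the anxiety time points in the Aim 2 paragraph.

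The cost is a few sentences and one degree of freedom. No new data are needed, although the plan should say how a missing baseline score will be handled.

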### **Aim 2: Determine the effect of the P3 mobile app on parental preparation for decision-making.**

Study procedure, participants, and data management are the same as described for Aim 1.

*Data collection.* Participant decision self-efficacy will be assessed at study entry and exit. Preparation for decision-making and anxiety will be in conjunction with the knowledge questionnaire at 25, 30 and 34 weeks.

### **Study measures**

*Decision Self-Efficacy Scale* is an 11-item scale that measures self-confidence or belief in one's abilities in decision-making, including shared decision-making.

*Preparation for Decision Making scale* is a 10-item scale that assesses how useful a decision-support intervention is in preparing the respondent to communicate with their clinician about a health decision. It has been shown to discriminate between patients who did and did not find a decisional aid helpful with a difference of 0.6 points on a 1-5 scale, and  $SD \approx 1.0$ . It can be customized to represent the particular intervention and decision under consideration; in this case, decisions about resuscitation, hospital choice, and breastfeeding are focused on during appropriate time points.

*PROMIS Anxiety Computerized Adaptive Test (CAT)* measures general anxiety over the past seven days. With CAT administration, participant responses guide the system's choice of subsequent items to enable a highly precise score with just ~5 items answered for most participants. PROMIS measures have evidence for validity in the general population and provide a T-score, where 50 (SD 10) corresponds to the US average.

### **Sample size**

The analytic sample size of 100 provides 80% power to detect a difference of 0.6 points in Preparation for Decision Making (using  $SD=1.0$ ), which was previously shown to be a meaningful difference for this scale. With 50 partners enrolled, a within-couple difference in Preparation for Decision Making of 0.4 points will be detectable with 80% power if the within-couple correlation is 0.5 or higher.

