## STUDY APPROACH

### Sample

Participants will be recruited from the obstetric clinics at the Froedtert Lutheran Memorial Hospital (FLMH), which is the adult tertiary care hospital co-located on the Milwaukee County campus with Children's Hospital of Wisconsin. FLMH is the primary teaching hospital for the Medical College of Wisconsin and it has a multi-state referral base, a high-risk pregnancy center, fetal intervention program, and a fertility clinic.

Inclusion criteria: Eligible participants will be (1) pregnant women, including pregnant minors aged 13 and above, (2) with presence of one of the following maternal preterm birth risk factors: history of spontaneous preterm birth, shortened cervical length, multiple gestation, fetal growth restriction, chronic hypertension, history of preeclampsia, and/or diabetes requiring medications, (3) with fetal GA between 14-21 weeks at enrollment to allow parents time to review the study information before birth, while also approaching a GA when neonatal resuscitation is an option (22 weeks), (4) who have a smartphone, and (5) who are able to read and speak English (the P3 mobile education is currently only available in English). For all women (or pregnant teenagers) who are eligible and agree to participate, we will invite their partner to participate; however, partner participation is not required. Partner is defined as the mother's primary pregnancy support person; in the majority of cases this is the father of the baby.

Exclusion criteria: Pregnancies with known significant birth defects will be excluded as information provided to these parents is different.

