## **Sample Size**

Based on our published data for knowledge of long-term outcomes, we expect average parent knowledge of seven long-term outcomes of 50% (SD 35%) in the ACOG group. In our population, English literacy is ~90% while ~80% possess smartphones. With 50 participants in each group, we can detect a 20% difference in knowledge, with power of 80% and  $\alpha$  of 0.05. To allow for 10% attrition, 55 pregnant participants will be enrolled in each group.

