### **Data analysis**

Preparation for decision making mean scores will be compared post-intervention at each time point across the two groups using Student's T-test. Associations between participant preparation scores, their level of domain specific knowledge, and socio-demographics will be explored using regression analyses. The primary analysis

will be focused on the pregnant women (or minors), with secondary analyses comparing between partners, and partners and women (or minors) within couples using paired T-tests.

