#### *Addressing Missing Data.*

Despite our best efforts to prevent study dropout and missing data, we anticipate there will be some study dropout. If one member of a couple decides to drop out, we will try to retain the other member. We will attempt to describe differences among those who do and do not drop out, with the goal of characterizing the uncertainty created by missing data. We will explore whether certain characteristics are more prevalent among participants who drop out, e.g., high anxiety or neonatal death.

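### The 80% power for the within-couple comparison counts enrolled partners, not complete pairs; with 45 pairs it is about 75% at correlation 0.5

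*Combined protocol and SAP*

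**What the plan says.** The Aim 2 sample size section makes two power statements. The first concerns the women: "The analytic sample size of 100 provides 80% power to detect a difference of 0.6 points". That number is net of loss, because the Aim 1 sample size section starts from 50 analysed per group and adds an allowance: "To allow for 10% attrition, 55 pregnant participants will be enrolled in each group". The second concerns couples: "With 50 partners enrolled, a within-couple difference in Preparation for Decision Making of 0.4 points will be detectable with 80% power", with the condition "if the within-couple correlation is 0.5 or higher".

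The Aim 2 data analysis section lists, among the secondary analyses, comparisons of "partners and women (or minors) within couples using paired T-tests". The section on missing data expects some dropout and says: "If one member of a couple decides to drop out, we will try to retain the other member". The section on the sample says that all partners will be invited but that "partner participation is not required". No attrition rate is given for partners or for couples, and no partner recruitment target is set.

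**The concern.** The two statements stand next to each other on different bases: the first uses an analysed number, the second an enrolled number. A paired test drops every couple with a missing score on either side. Keeping the remaining member in the study helps the between-group comparisons but does not restore the pair. Fifty enrolled partners therefore give 50 usable pairs only if no partner, and no woman with an enrolled partner, is missing at the time point analysed.

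At stake is a secondary power statement. If it is too high, a null within-couple result could be read as stronger evidence of no difference than the data support.

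**Working it through.** **Inputs**
- Difference δ = 0.4 points, 50 partners, 80% power and correlation ρ = 0.5 as the lower limit: Aim 2 sample size section.
- SD = 1.0: stated there for the between-group comparison; assumed here for both members of a couple.
- α = 0.05: stated in the Aim 1 sample size section; assumed to carry over. Two-sided testing is also assumed. A one-sided test with 50 pairs would give 87.4%, so two-sided is the version that matches the stated 80%.
- Attrition of 10%: stated for pregnant participants only; applied here to couples as an assumption.

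**Formulas**
- SD of the difference: SD_d = SD × √(2(1 − ρ)). At ρ = 0.5 this is 1.0 × √1 = 1.0.
- Normal approximation: power = Φ(δ√n / SD_d − 1.96).
- Exact: noncentral t with n − 1 degrees of freedom and noncentrality δ√n / SD_d.

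**The plan's own figure, 50 complete pairs**
- 0.4 × √50 = 2.828, and Φ(2.828 − 1.96) = 80.7%. Exact t: 79.2%.
- Pairs needed for 80%: (1.96 + 0.8416)² / 0.4² = 49.06, so 50 by the normal approximation. By exact t, 51 pairs give 79.99%.

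The stated 80% is reproduced and uses all 50 pairs.

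**After loss of pairs**
- 10% of couples lost: 50 × 0.90 = 45 pairs. 0.4 × √45 = 2.683, and Φ(2.683 − 1.96) = 76.5%. Exact t: 74.7%.
- Each member lost independently at 10% (a further assumption, not in the documents): 50 × 0.90 × 0.90 = 40.5, so 40 to 41 pairs.

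| Complete pairs | Power for 0.4 points, ρ = 0.5 (t / normal) | Difference detectable at 80%, ρ = 0.5 (t / normal) | ρ needed for 80% at 0.4 points (t / normal) | Power, ρ = 0.6 (t) |
|---|---|---|---|---|
| 50 | 79.2% / 80.7% | 0.404 / 0.396 | 0.51 / 0.49 | 87.3% |
| 45 | 74.7% / 76.5% | 0.427 / 0.418 | 0.56 / 0.54 | 83.5% |
| 40 | 69.4% / 71.6% | 0.454 / 0.443 | 0.61 / 0.59 | 78.8% |

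**Partners needed to keep the claim after a 10% loss of pairs**
- For 50 complete pairs: 50 / 0.9 = 55.6, so 56 enrolled.
- For 51 complete pairs: 51 / 0.9 = 56.7, so 57 enrolled.

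**The case against.** The strongest reply is that the fault is one loose word. Fifty is half of the analysed 100, so the authors may have meant that half of the analysed women have a participating partner. On that reading the 80% is right, and only the word for enrolment is wrong. The documents do not settle this. Either way the sentence as written does not hold and needs the same edit.

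Other points have weight but do not remove the problem:
- **More than 50 partners may enrol.** All are invited. In the pilot 10 fathers and 18 mothers completed the final survey. At that ratio 100 women would bring 100 × 10/18 ≈ 56 partners, and 56 complete pairs give about 84% (exact t) at correlation 0.5. The pilot was small and followed participants for four weeks, and the plan's claim is made for 50.
- **The 10% is borrowed.** This is true, and it must be labelled as an assumption. But the women are half of every pair. If those with partners drop out at the plan's own rate, 45 pairs remain even with no partner loss.
- **Loss depends on the time point.** A couple that leaves after 25 weeks still counts at 25 weeks. The 10% is the allowance behind the 25-week primary analysis, so later time points would be expected to lose at least as many pairs.
- **The gap is within the uncertainty of the inputs.** The scale's SD is given only approximately. With SD 0.95, 45 pairs give 78.9% (t) or 80.6% (normal) at correlation 0.5. A correlation of about 0.56 also closes the gap. Neither is the stated condition, which promises 80% from correlation 0.5 upward.

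**Conclusion.** The point holds. At the stated lower limit of the correlation, the claimed 80% needs essentially all 50 enrolled partners to form complete pairs, and the plan itself expects losses. A 10% loss of couples costs about 4 points of power (79.2% to 74.7% by exact t; 80.7% to 76.5% by the normal approximation). Put another way, the detectable difference rises from 0.40 to about 0.43 points. These figures rest on SD 1.0 in both members, two-sided α of 0.05, and the women's attrition rate applied to couples.

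This is not an arithmetic error: an enrolled count stands where an analysed count is needed. The effect is small and confined to a secondary analysis. The primary outcome, the comparison between groups of women and the enrolment of 110 do not change.

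**What to change.** Rewrite the sentence in the Aim 2 sample size section so that it rests on complete pairs, and state the loss assumed for couples. Any one of these would do:

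1. With 50 partners enrolled and about 45 complete pairs after an assumed 10% loss, a within-couple difference of about 0.43 points is detectable with 80% power at correlation 0.5.
2. Keep 0.4 points with about 45 complete pairs, but make the statement conditional on a correlation of about 0.56 or higher.
3. Base the statement on 50 complete couples, and note that this corresponds to about 56 to 57 partners enrolled if 10% of pairs are lost.

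The cost is one sentence. The first two options change only the stated detectable difference or the condition on the correlation. The third makes explicit how many partners the claim depends on.
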